4.1.1 GLOMERULAR FILTRATION RATE

We will estimate the GFR using the modification of diet in renal disease (MDRD) formula:

$$\text{GFR} = 175 \times \text{SerumCr}^{-1.154} \times \text{age}^{-0.203} \times 1.212 \text{ (if patient is African American)} \times 0.742 \text{ (if female)}$$

4.2 SECONDARY ENDPOINTS

Major secondary endpoints will include:

[figure not shown]
- 1- Incidence of CIN, defined as an increase in baseline serum creatinine of 25% or ≥ 0.5 mg/dl 48 to 72 hours post-percutaneous angiography
- 2- Safety profile of the interventions including volume overload, hypotension, headache, medication interaction, the need for hemodialysis, intra-aortic balloon pump, endotracheal intubation or the use of vasopressors.
- 3- Analysis and comparison to a CIN predictive score calculator (Mehran Score).

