4.1 PRIMARY ENDPOINT

The primary endpoint for this trial will be to determine the change in glomerular filtration rate after exposure to contrast media. We will compare the change in GFR before and after percutaneous angiography of the group that received intravenous nitroglycerin with the change in GFR before and after percutaneous angiography of the group that did not receive intravenous nitroglycerin.

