5.0 RESEARCH DESIGN AND METHODS

5.1 SAMPLE SIZE

NOT A CASE CONTROL STUDY. This is a randomized, placebo-controlled clinical trial with a 1:1 randomization of active therapy to placebo. Prior data from our retrospective study indicate that the failure rate among controls is 0.3. If the true relative risk of failure for experimental subjects relative to controls is 0.5, we will need to study 161 experimental subjects and 161 control subjects to be able to reject the null hypothesis that this relative risk equals 1 with probability (power) 0.9. The Type I error probability associated with this test of this null hypothesis is 0.05.

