5.2.3 EXCLUSION CRITERIA

None of the following exclusion criteria must be present for the patient to be enrolled in the trial

- 1- Patients on renal replacement therapy before randomization, will be excluded.
- 2- Being exposed to any types of nitrates 48 hours prior to randomization,
- 3- History of allergic reaction to any of the components of intravenous nitroglycerin.
- 4- Exposure to contrast media 4 days prior randomization.
- 5- Planned revascularization in the next 24 to 48 hours of the first PCI procedure.
- 6- The patient is hypotensive (<90/60mmHg) at the time of randomization.
- 7- Patients exposed to phosphodiesterase inhibitors 48 hours prior to randomization

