5.3 STUDY ALGORythM

To achieve our primary and secondary end-points we will (1) screen patients in the catheterization lab and/or emergency department of Mount Sinai Medical Center. (2) After inclusion and exclusion criteria's are verified, informed consent will be signed by the patient. (3) a case report form will be completed. (4) The research staff will order a treatment protocol to be administered. (5) Laboratory studies will be performed if needed. (6) The patients will receive an intravenous infusion of nitroglycerin and/or saline for at least 1 hour. (7) Coronary angiography will be performed and another screening for exclusion criteria will be done by the coordinator and assistant investigators. (8) Variables such as volume of contrast and number of vessels stented will be obtained. (9) Patients will go to recovery area and another infusion will be started for another 3 hours. (10) 48 hours later patient will be contacted to come to the hospital for another set of laboratory studies or patients that stayed in the hospital will be contacted and all the information needed will be completed.

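### CIN and eGFR change are scored from the follow-up creatinine alone, so a patient dialysed before that sample can be recorded as free of CIN, with a stable or improved eGFR

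*Combined protocol and SAP*

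**What the plan says.** - **CIN (4.2, first secondary endpoint)** is "defined as an increase in baseline serum creatinine of 25% or ≥ 0.5 mg/dl 48 to 72 hours post-percutaneous angiography". The Executive Summary gives the same thresholds without the time window. Creatinine is the only component.
- **Primary endpoint (4.1):** "The primary endpoint for this trial will be to determine the change in glomerular filtration rate after exposure to contrast media", compared between arms. No time point is given.
- **How GFR is obtained (4.1.1):** "We will estimate the GFR using the modification of diet in renal disease (MDRD) formula". Age, sex and race are in effect fixed over a few days, so creatinine is the only input that moves.
- **Follow-up sample (5.3):** "48 hours later patient will be contacted to come to the hospital for another set of laboratory studies", or the information is completed in hospital for patients still admitted. No other post-procedure laboratory set is scheduled.
- **Dialysis after the procedure (4.2, second secondary endpoint)** is a safety item: "the need for hemodialysis, intra-aortic balloon pump, endotracheal intubation or the use of vasopressors".
- **Exclusion (5.2.3):** "Patients on renal replacement therapy before randomization, will be excluded". Patients who first need dialysis after randomization therefore stay in the trial.

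No section says how a patient dialysed before the follow-up sample is scored for CIN or for eGFR.

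**The concern.** Dialysis removes creatinine from the blood. A value drawn after dialysis no longer measures kidney function, yet both efficacy endpoints would take it at face value. The patient with the worst kidney outcome could then be counted as a success for CIN and contribute a favourable eGFR change. Reporting dialysis under safety records the event but does not correct the CIN rate or the mean eGFR change.

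The trial enrols patients at raised risk (Mehran score of at least 6), and the score in 4.2.1 allots points for GFR below 20, so the situation is plausible here. If such patients were unevenly spread between arms, the CIN comparison would be biased: towards nitroglycerin if they fell mostly in that arm, and against it if they fell mostly among controls.

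**Working it through.** **1. The plan's own figure.** Section 5.1 states that "the failure rate among controls is 0.3" and continues: "If the true relative risk of failure for experimental subjects relative to controls is 0.5". This gives 0.30 versus 0.15, with power 0.9 and type I error 0.05. Two-sided, pooled variance, no continuity correction, mean rate 0.225:

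n = [1.960·√(2·0.225·0.775) + 1.282·√(0.30·0.70 + 0.15·0.85)]² / 0.15² = 160.8, so 161 per arm.

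This matches the stated 161. Power is 0.900 at 161 per arm and 0.951 at the planned 200 per arm. Nothing below makes that arithmetic wrong.

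**2. One patient under the stated rules.** The formula in 4.1.1 for a man who is not African American is eGFR = 175 × Cr^-1.154 × age^-0.203. Ages and creatinine values are illustrative assumptions.

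| | Creatinine (mg/dl) | eGFR | Change | CIN by 4.2 |
|---|---|---|---|---|
| A, age 70: baseline | 2.5 | 25.7 | | |
| A: peak, no dialysis | 4.5 | 13.0 | -12.6 | yes |
| A: sampled after dialysis | 2.2 | 29.7 | +4.1 | no |
| B, age 75: baseline | 2.0 | 32.7 | | |
| B: peak, no dialysis | 4.0 | 14.7 | -18.0 | yes |
| B: sampled after dialysis | 1.8 | 37.0 | +4.2 | no |
| B: sampled after dialysis | 2.0 | 32.7 | 0.0 | no |
| B: sampled after dialysis | 2.4 | 26.5 | -6.2 | no (+20%, +0.4) |

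The swing between the peak and the lowest post-dialysis value is 16.7 for patient A and 22.3 for patient B (mL/min/1.73 m²).

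**3. When the misscoring occurs.** For patient A the 0.5 mg/dl limb is reached at 2.5 + 0.5 = 3.0. A sampled value of 3.0 or more is still CIN. A value between 2.5 and 3.0 is scored as no CIN but still shows an eGFR decline. An improved eGFR needs a value below 2.5, a fall of more than (4.5 - 2.5)/4.5 = 44% from the peak.

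**4. Effect on an arm's mean eGFR change.** Shift = share affected × swing. The share is assumed.

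| Share affected | Swing 16.7 (A) | Swing 22.3 (B) |
|---|---|---|
| 1% | 0.17 | 0.22 |
| 2% | 0.33 | 0.45 |

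**5. Effect on CIN.** The starting point is 0.30 versus 0.15. The assumed share is of all patients in the named arm, each taken to be dialysed before the sample and brought below threshold.

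| Missed cases | Observed rates (control, nitroglycerin) | RR | Power, 161 per arm | Power, 200 per arm |
|---|---|---|---|---|
| None | 0.30, 0.15 | 0.500 | 0.900 | 0.951 |
| 1% of controls, proportional to CIN | 0.29, 0.145 | 0.500 | 0.887 | 0.943 |
| 2% of controls, proportional to CIN | 0.28, 0.14 | 0.500 | 0.873 | 0.933 |
| 1%, controls only | 0.29, 0.15 | 0.517 | 0.862 | 0.925 |
| 2%, controls only | 0.28, 0.15 | 0.536 | 0.813 | 0.889 |
| 1%, nitroglycerin only | 0.30, 0.14 | 0.467 | bias towards drug | bias towards drug |
| 2%, nitroglycerin only | 0.30, 0.13 | 0.433 | bias towards drug | bias towards drug |

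The one-arm rows are extremes; the proportional rows are the milder case.

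**The case against.** The strongest reply is that the problem is rare and conditional. Three things must happen before a sample at about 48 hours: a severe rise, the start of dialysis, and a fall below the threshold. Catheterization patients from the emergency department are to be non-emergent, and prior renal replacement is excluded. The documents give no rate or timing of dialysis; its place in a safety list does not show that the sponsor expects it. Even with 2% lost from one arm, a difference of 28% versus 15%, or 30% versus 13%, at 200 per arm gives z of about 3.2 or 4.1, against 3.6 for the planned rates. An imbalance in dialysis would also show in the safety results and to the DSMB, which sees unblinded data (3.2.3). All of this stands, and it limits the size of the point. It does not change how an affected patient is scored.

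Three stronger readings are tempting and are not supported:

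- A reader might infer that every dialysed patient is misclassified. Step 3 shows otherwise: the score depends on how far creatinine has fallen when sampled.
- A reader might infer that the 48 to 72 hour window governs both endpoints. It is written only for CIN. The link from eGFR to the sample at about 48 hours is an inference from 5.3, and the missing time point in 4.1 is a gap of its own.
- A reader might infer that the repair needs no new data. Section 5.3 schedules one post-procedure laboratory set, and 5.2.4 lists only a baseline and a post-procedure creatinine. No pre-dialysis value and no time of dialysis is planned. A plain rule of carrying forward the last value before dialysis could therefore fall back on baseline and score a dialysed patient as unchanged.

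**Conclusion.** The point holds in conditional form. As written, 4.1 and 4.2 can score a patient dialysed before the follow-up sample as free of CIN, with a stable or improved eGFR, because both endpoints read only the follow-up creatinine and dialysis is carried only under safety. This is more than a missing detail: a stated definition, applied literally, can give the wrong answer for the worst kidney outcome.

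The size is probably small. At assumed rates of 1% to 2% an arm's mean eGFR change moves by roughly 0.2 to 0.45 mL/min/1.73 m². If missed cases are proportional to CIN, the relative risk is unchanged and power at 200 per arm falls only from 0.951 to between 0.933 and 0.943. Material bias in the CIN comparison needs the losses to be concentrated in one arm, for which the documents give no evidence. The dialysis rates and creatinine values are assumptions throughout. The case for change rests on the direction of the error and the low cost of preventing it, not on a threat to the sample size, which reproduces.

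**What to change.** Make these changes before any unblinded look at the outcomes:

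- **4.2:** count any patient who starts renal replacement therapy after randomization and before the outcome sample as CIN.
- **4.1:** state that the follow-up eGFR comes from the 48 to 72 hour sample and that a post-dialysis creatinine is not used. If a post-procedure creatinine before dialysis exists, use the last one; otherwise assign the worst rank, and never the baseline value. Section 4.1 names no test. A worst rank fits a rank-based comparison directly; if means are to be compared, 4.1 must also say in advance what number stands for it.
- **Sensitivity analysis:** rank every patient dialysed before the sample as the worst outcome.
- **Case report form:** record the date and time of first dialysis and any clinical creatinine drawn before it.

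The cost is a few sentences and a few data fields, with no change to care. The downside is that CIN becomes slightly broader than a pure creatinine event and may include dialysis started for another reason, such as volume overload.

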4.2.1 MEHRAN SCORE

According to a validated score proposed by Mehran et al. patients with a score equal or greater than 6, has a 14% chances or more of developing CIN (21). We will use this value to recruit patients with a high probability of developing CIN. The score will be calculated using the following variables: hypotension (5 points for BP $<80/60$ mmHg), intra-aortic balloon pump use before during or after the procedure (5 points), congestive heart failure (5 points for New York Heart Association Class II-III, history of pulmonary edema or an ejection fraction $<40\%$) age >75 years (4 points), anemia (3 points for hematocrit $<39\%$ for men and $<35\%$ for women), diabetes mellitus (3 points), serum creatinine >1.5 (4 points), GFR <60 (2 points for 41-60; 4 points for 21-40 and 6 points for <20) and contrast volume used (1 for each 100 cc).

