5.2.2 INCLUSION CRITERIA

All of the following inclusion criteria must be present for the patient to be enrolled in the trial.

- 1- Patient must be scheduled for percutaneous angiography, defined as diagnostic cardiac catheterization, or lower extremity or aortic iodinated contrast angiography.
- 2- Patients must have a Mehran score of at least 6 before the procedure.
- 3- Patients must have baseline creatinine and hemoglobin drawn before the procedure.
- 4- Signed informed consent.

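### The printed Mehran score that decides entry is not monotone: NYHA class IV is not named and a GFR of 20 falls in no band

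*Combined protocol and SAP*

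**What the plan says.** Section 5.2.2 item 2 makes the score an entry condition: "Patients must have a Mehran score of at least 6 before the procedure". Sections 4.3 and 5.2.1 repeat the cut-off, and section 4.2 makes comparison with the score its third secondary endpoint. Section 4.2.1 sets out the points:

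- Heart failure: "5 points for New York Heart Association Class II-III, history of pulmonary edema or an ejection fraction" below 40%. These are three alternative routes to the same 5 points. Class IV is not among them.
- Renal function: "serum creatinine >1.5 (4 points), GFR <60", with the GFR item split into "2 points for 41-60; 4 points for 21-40 and 6 points for <20".
- Age and diabetes: "age >75 years (4 points") and "diabetes mellitus (3 points").
- Anemia: "anemia (3 points for hematocrit" below 39% in men and 35% in women).

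For laboratory data, 5.2.2 item 3 says: "Patients must have baseline creatinine and hemoglobin drawn before the procedure". The variable list in 5.2.4 likewise has hemoglobin and no hematocrit. Neither 4.1.1, which gives the MDRD formula, nor 4.2.1 says whether eGFR is rounded before it is banded.

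**The concern.** A risk score used as an entry threshold should not fall as the patient's condition worsens. Taken at its word, 4.2.1 lets it fall in two places: between NYHA class III and class IV, and at the edges of the GFR bands. Section 4.2.1 says the cut-off is there to recruit patients likely to develop CIN, so a rule that can refuse the sicker of two otherwise identical patients works against its purpose. Staff who notice the gaps may fill them differently from one patient to the next. That would make eligibility inconsistent and blur the comparison of observed CIN with the score.

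The exclusion criteria do not make the matter moot. Section 5.2.3 excludes patients on renal replacement therapy but names neither class IV nor low GFR, and 5.4 provides for patients in acute congestive heart failure.

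**Working it through.** The plan gives no worked score to reproduce, so the check adds the printed points. Contrast volume, balloon pump and hypotension are set to 0 throughout, to leave the items that can be known at screening.

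**Heart failure.** Take ejection fraction of 40% or more and no past pulmonary edema. Class II-III scores 5 and class IV scores 0. With one further item:

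| Other item | Class III | Class IV |
|---|---|---|
| Diabetes (3) | 5 + 3 = 8, enters | 0 + 3 = 3, fails |
| Age over 75 (4) | 5 + 4 = 9, enters | 0 + 4 = 4, fails |
| GFR 41-60, creatinine 1.5 or less (2) | 5 + 2 = 7, enters | 0 + 2 = 2, fails |

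Crossing age, anemia and diabetes (each present or absent) with renal totals of 0, 2, 8 or 10 gives 2 × 2 × 2 × 4 = 32 profiles. In 6 of them class III enters and class IV fails. These are combinations on a chosen grid, not patient frequencies.

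**GFR at 20.** Inputs are the MDRD formula in 4.1.1 and a 70-year-old man without the race multiplier or any other scored item:

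eGFR = 175 × Cr^(−1.154) × 70^(−0.203) = 175 × 0.4221 × Cr^(−1.154) = 73.87 × Cr^(−1.154)

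Creatinine above 1.5 gives 4 points in every row. The totals add the GFR points to these 4.

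| Creatinine | Cr^(−1.154) | eGFR | Total, eGFR rounded | Total, eGFR unrounded |
|---|---|---|---|---|
| 2.9 | 0.2927 | 21.6 | 4 + 4 = 8 | 4 + 4 = 8 |
| 3.0 | 0.2815 | 20.8 | 4 + 4 = 8 | 4 + 0 = 4 |
| 3.1 | 0.2710 | 20.0 | 4 + 0 = 4 | 4 + 0 = 4 |
| 3.2 | 0.2613 | 19.3 | 4 + 6 = 10 | 4 + 6 = 10 |

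Under either convention the patient is eligible, then ineligible, then eligible again as renal function worsens. Only the width of the gap changes: rounded, it holds the value 20; unrounded, it holds everything from 20 to below 21.

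**How often GFR 20 decides entry.** Solving the formula for creatinine at eGFR 20, over ages 40 to 100, both sexes and with or without the race multiplier, gives 2.25 to 4.04 mg/dl. This is always above 1.5, so the creatinine item always gives 4. The smallest other item (diabetes or anemia) is worth 3, and 4 + 3 = 7 passes. Of the 2 × 2 × 2 × 2 = 16 combinations of heart failure, age, anemia and diabetes, only the one with none of them fails.

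**GFR between 40 and 41.** This gap exists only if eGFR is not rounded. For the same man:

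- creatinine 1.6: 73.87 × 0.5814 = 42.9, total 4 + 2 = 6
- creatinine 1.7: 73.87 × 0.5421 = 40.04, total 4 + 0 = 4
- creatinine 1.8: 73.87 × 0.5075 = 37.5, total 4 + 4 = 8

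Rounding moves 40.04 to 40, into the 4-point band, and the middle total becomes 8.

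**Anemia.** The item is worth 3 points, half the cut-off. If it goes unscored because hematocrit was not recorded, a patient with diabetes and anemia only drops from 3 + 3 = 6 (enters) to 3 (fails). This is a data gap and not a reversal in the scale.

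**The case against.** Several stronger readings are tempting, and the documents do not support them.

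- *Class IV never scores.* It does: an ejection fraction below 40% or past pulmonary edema earns the same 5 points. Only class IV without either scores 0.
- *GFR 20 scores nothing.* It loses only the GFR points. The creatinine item still gives 4, and any one further item secures entry.
- *The 8, 4, 10 sequence follows from the text alone.* It needs two assumptions: rounding to whole numbers, and adding creatinine and GFR points. Section 4.2.1 lists them as separate items, which favors adding, but does not say so outright. If only the larger of the two counted, the rounded totals at creatinine 3.0, 3.1 and 3.2 would be 4, 4 and 6. There would be no drop from GFR 21 to 20, although GFR 20 would still be in no band.
- *The anemia item makes sicker patients score lower.* It does not. Hematocrit is not barred, only not listed, and the blood count that gives hemoglobin can supply it.
- *The 14% risk attached to the cut-off no longer holds, or the score was copied wrongly.* Either claim needs the cited source (reference 21), which cannot be checked from these documents.
- *The trial result is biased.* The score is applied before randomization and in the same way for everyone, so the comparison of change in GFR between arms is unaffected. The gaps only withhold points. They can turn away patients but admit nobody who would otherwise fall short.

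All these limits stand, and they keep the point small. They do not remove the two gaps, which are visible on the face of 4.2.1.

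**Conclusion.** The score as printed in 4.2.1 is not monotone. Class IV with ejection fraction of 40% or more and no past pulmonary edema scores 0 against 5 for class II-III, enough to reverse eligibility (3 against 8 with diabetes only). A GFR of 20 lies in no band; without rounding, neither do values from 20 to below 21 or between 40 and 41. The class IV result rests on a literal reading of the item. The eligible-ineligible-eligible pattern around GFR 20 rests on adding creatinine and GFR points and holds with or without rounding; the exact totals of 8, 4 and 10 at creatinine 3.0, 3.1 and 3.2 also need rounding.

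The consequence is possible exclusion or inconsistent scoring of some high-risk patients the trial wants, and some noise in the third secondary endpoint. The documents give no distribution of NYHA class or GFR, so the number affected is unknown. Severity: minor.

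**What to change.** In 4.2.1, check each item against the cited score (reference 21) and correct the text so that:

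1. NYHA class IV is explicitly assigned in the heart-failure item;
2. every GFR below 60 falls in exactly one band;
3. a rounding rule for eGFR is stated.

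It would help to say in the same place whether creatinine and GFR points are added. As a smaller accompanying change, reconcile the hematocrit-based anemia item with 5.2.2 item 3 and 5.2.4 by recording hematocrit from the blood count that gives the hemoglobin.

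The cost is wording and case report form fields. No extra patients or visits are needed, and the 161 per arm in 5.1 is untouched because that calculation does not use the score.

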4.3 SAMPLE AND METHODOLOGY

We will enroll 400 patients with a Mehran score of 6 or more that have a pre-procedural creatinine measured. Following baseline assessments, patients will be randomly assigned to receive intravenous infusion nitroglycerine plus intravenous normal saline or normal saline only.

5.0 RESEARCH DESIGN AND METHODS

5.1 SAMPLE SIZE

NOT A CASE CONTROL STUDY. This is a randomized, placebo-controlled clinical trial with a 1:1 randomization of active therapy to placebo. Prior data from our retrospective study indicate that the failure rate among controls is 0.3. If the true relative risk of failure for experimental subjects relative to controls is 0.5, we will need to study 161 experimental subjects and 161 control subjects to be able to reject the null hypothesis that this relative risk equals 1 with probability (power) 0.9. The Type I error probability associated with this test of this null hypothesis is 0.05.

5.2 STUDY POPULATION

5.2.1 PATIENT RECRUITMENT

The recruitment strategies for CoNaN trial are targeted to specific groups in order to meet study goals with respect to patient enrollment and demographics. Meeting these goals, which results in a study population that reflects the typical patient population with the disease/health characteristics of interest, is necessary for making informed conclusions based on data collected during the study.

CoNaN trial will randomize 400 patients with a Mehran score ≥ 6 in a 1 x 1 trial of intravenous nitroglycerin versus intravenous saline only. All patients must complete informed consent process prior to being randomized into the trial.

Patients will be recruited primarily from 2 different sites. (1) Mount Sinai Emergency department, once they are evaluated by cardiology and scheduled for a non-emergent catheterization. (2) Directly from the Mount Sinai Medical Center catheterization Laboratory.

